4.1 Design

This is an exploratory pilot trial. The subject population to be studied are those who have been on chronic hemodialysis for ≥ 3 months with recurrent intradialytic weight gain >0.04 kg/kg body weight.

[figure not shown]
Regional myocardial wall abnormalities and biomarker measurements will be compared pre and post hemodialysis with standard heparin anticoagulated hemodialysis treatment and after one hemodialysis treatments with the regional citrate anticoagulated SCD device.

[figure not shown]
Two different treatment regimens are planned for this clinical trial.

Treatment 1 will be a 5 hour hemodialysis treatment session utilizing heparin anticoagulation. The first hour will utilize a blood flow rate (BFR) of 300 mL/min and a dialysate flow rate (DFR) of 600 mL/min with no ultrafiltration (UF). After the first hour, the blood flow rate will be adjusted to 200 mL/min with a dialysate flow rate of 400 mL/min. This BFR and DFR will be maintained for the remaining 4 hours of the 5 hour session.

Treatment 2 will be a 5 hour hemodialysis treatment session. The first hour will be undertaken with heparin anticoagulation utilizing a BFR of 300 mL/min and a dialysate flow rate of 600 mL/min with no UF. After the first hour, the SCD will be integrated into the circuit with regional citrate anticoagulation and BFR adjusted to 200 mL/min with a DFR of 400 mL/min. This BFR and DFR with RCA will be maintained for the last 4 hours of the 5 hour session.

Of importance, this 5 hour session is planned to ensure adequate solute clearance but with only 4 hour high UF to achieve the patients dry weight.

The hemodialysis treatments will be performed at the Acute Dialysis Unit, University of Michigan.

4.2 Number of Subjects

10 Subjects will be studied in this protocol.

4.3 Duration of Study

The total duration of participation will be approximately 3 weeks.

5. Subject Selection

5.1 Inclusion Criteria

- 5.1.1 End-stage renal disease (CKD Stage 5)
- 5.1.2 Receiving chronic hemodialysis thrice weekly for ≥ 3 months
- 5.1.3 Current dialysis access is a well-functioning arteriovenous (AV) graft, AV fistula, or cuffed tunneled catheter (average blood flow >350 ml/min in the last 3 HD sessions)
- 5.1.4 Patient can safely receive chronic hemodialysis thrice weekly with heparin anticoagulation
- 5.1.5 Patient has achieved $Kt/V \geq 1.2$ over the preceding 2 months
- 5.1.6 Patient has no contraindication for regional citrate anticoagulation
- 5.1.7 Baseline blood pressure before hemodialysis has been $\geq 100/50$ over preceding 4 weeks
- 5.1.8 Recurrent intradialytic weight gain >0.04 kg/kg body weight at the beginning of the week (i.e. Monday or Tuesday). Recurrent is defined as at least two of eight sessions the past 60 days or at least three of twelve sessions the past 90 days.
OR
Intradialytic hypotension (IDH) prone (IDH greater than 30% of dialysis sessions in month before session) IDH defined as systolic blood pressure

(SBP) less than 100 mmHg or SBP decrease greater than >10% of predialysis with symptoms

5.1.9 Able to and have given informed consent

5.1.10 Age \geq 18 years

5.2 Exclusion Criteria

5.2.1. Human immunodeficiency virus (HIV) 1 or 2 Ab (+)

5.2.2. Any active inflammatory condition (e.g., gout, systemic lupus erythematosus flare, hepatitis B or C infection, allograft rejection, subcutaneous injection of illicit drugs, “skin popping”)

5.2.3. Treatment with immunosuppressive therapy (e.g., anti-neoplastic agents, glucocorticoids, calcineurin inhibitors) within 30 days of the treatment program

5.2.4. Hemoglobin (Hgb) <9 g/dL

5.2.5. Platelet count $<50,000/\text{mm}^3$

5.2.6. WBC $<4,000/\text{mm}^3$

5.2.7. Acute coronary syndrome, including myocardial infarction within 90 days of the treatment period

5.2.8. Ischemic cardiomyopathy

5.2.9. Participation in an experimental drug or device study, within 30 days of the treatment period

5.2.10. Woman who is pregnant, breast feeding a child, or is trying to become pregnant

5.2.11. Inability to comply with Study Procedures

5.2.12. Exposure to hemodialysis for less than 90 days

5.2.13. Severe heart failure (NY Heart Association functional class greater than or equal to 3)

- 5.2.14 Cardiac transplant recipient
- 5.2.15 Mental incapacity to consent
- 5.2.16 Positive test for active infection with COVID-19 virus

6. Study Materials

6.1 Study Materials Packaging and Storage

All non-routine supplies and components needed to administer SCD treatments will be stored in a secure, limited-access area.

6.2 Use of the SCD

Personnel at the University of Michigan dialysis unit will be responsible for administering SCD treatments under the supervision and guidance of the clinical investigators.

In this trial, “SCD treatment” using a two-cartridge system will be delivered using a type of dialysis equipment commonly used for conventional hemodialysis therapy. The SCD cartridge will be connected in line with the conventional hemodialysis system, and treatment will be delivered for the usual duration of patient treatment. Blood exchange will occur using the patient’s existing hemodialysis access (i.e., arteriovenous graft, arteriovenous fistula, or dialysis catheter).

6.2.1 SCD Set-up

Consult The Set Up Manual of Operations For Fresenius 2008T.

6.2.2 Vascular Access

The Subject’s current hemodialysis vascular access will be used for study hemodialysis treatments. The vascular access will be cannulated or accessed only by persons who are trained and experienced in this procedure.

6.2.3 Dialysate Fluid

The dialysate fluid during SHH and during the first hour of SCD treatment arm will be chosen by the Principal Investigator based on the Subject’s laboratory tests and clinical status. The content of the dialysate fluid may be adjusted as needed. For the next four hours of SCD treatment with citrate anticoagulation, 0 mM calcium dialysate will be used.

6.3 Selective Cytopheresis System Procedures

6.3.1 Description of SCD System

Dr. [name], Professor of Internal Medicine, and his group have developed a biomimetic membrane cell processing device, named the Selective Cytopheretic Device (SCD). This developing commercial product licensed to CytoPherx, Inc. (a University of Michigan spinoff) is identical to hemodialysis cartridges (F series) manufactured by Fresenius, AG except for a cartridge casing with closed end caps (U.S. patent 9,341,626). This device, when incorporated into an extracorporeal blood circuit, preferentially binds activated leukocytes (LE), and in the low calcium environment afforded by regional citrate anticoagulation (RCA), the bound LE are deactivated and released back to the systemic circulation. This device is identical to a polysulphone membrane dialyzer but with the blood flow path directed to the outside of the hollow fiber membrane rather than the inside of the membrane. The blood flow path results in low shear forces similar to capillary shear so the membrane has selectivity to bind activated LE. This continuous cell processing activity results in measurable diminution of excessive inflammatory responses in a variety of preclinical and clinical disorders.

The Selective Cytopheretic Device (SCD) investigational device to be used in the execution of this clinical trial protocol consists of two (2) devices packaged separately: 1) SCD Blood Tubing Set (Product Code 8X64R1) 2) SCD-F40 (Fresenius F40S). These two devices are connected in series to a Renal Replacement pump (a Fresenius 2008T ® RRT device). Blood from the Renal Replacement pump circuit is diverted after the hemodialysis dialyzer through the extra capillary space (ECS) of the SCD-F40. Blood circulates through this space and it is returned to the patient via the venous return line of the renal replacement therapy circuit. Regional citrate anticoagulation is used for the entire hemodialysis circuit and SCD blood circuits. When utilized with this flow pathway and in the presence of regional citrate anticoagulation, the SCD membrane binds activated leukocytes and modulates inflammation. Thus, the F40-SCD, and blood tubing are investigational- not FDA approved or cleared for marketing. The remainder of the system is commercially available, FDA cleared.

6.3.2 Intended Use

The SCD is intended to be used in conjunction with FDA-approved dialysis systems on ESRD patients who are already receiving chronic dialysis in the dialysis unit of the University of Michigan.

6.3.3 SCD System Perfusion Initiation Protocol

Procedural Overview

The preparation for hemodialysis with SCD integration is similar to that of the conventional dialysis blood lines by adding the SCD in series with the initial hemodialysis cartridge.

Aseptic technique must be used throughout the entire integration procedure. The SCD cartridge will be brought to the patient's bedside where the SCD blood line will be connected in series to the existing dialysis circuit. After one hour of hemodialysis the SCD will be integrated into the extracorporeal circuit, the dialysate pump system will be initiated and maintained by the trained personnel of the dialysis unit.

6.3.4 Citrate Anticoagulation Therapy

- ❖ Citrate acts as an anticoagulation agent by binding with calcium. The bound calcium is then unavailable to trigger clotting factors. A fixed blood flow to citrate flow ratio will be used to ensure strong anticoagulant activity (circuit ionized Ca < 0.4 mM) throughout the entire circuit
- ❖ The specific clinical protocol developed at Henry Ford Hospital by [name] (co-investigator) for citrate anticoagulation will be used. About 90-95 % of the free [citrate⁻ and complex [citrate-calcium]⁻ ions are cleared on the high flux and high efficiency OF250NR dialyzer using a commercial Fresenius calcium-free dialysis fluid at 400 ml/min dialysate flow rate. The remaining clinically negligible citrate enters the patient with the venous blood return and is metabolized in the liver. The very high citrate removal on the dialyzer is a unique feature of the IHD-RCA protocol and will prevent citrate accumulation in the patient even in the absence of body metabolism of citrate.
- ❖ The filter performance in removing citrate is indirectly monitored by online measurements of conductivity dialysance and by visual filter inspections for clotting.
- ❖ Anticoagulation is only reversed when calcium is added to the circuit venous bloodstream just before it is returned to the patient in order to restore systemic ionized calcium levels that will allow adequate systemic blood clotting and cardiac function.
- ❖ The initial calcium rate is selected from a table based on patient online hemoglobin (Crit-Line III) and last measured albumin level. The calcium infusion is adjusted hourly based on online hemoglobin values and every time a systemic ionized calcium measurement is performed.

SCD Citrate Dialysis Circuit on First Filter

[figure not shown]

Figure 2. Diagram of the first filter circuit for the HFH citrate protocol

❖ **IHD-RCA Protocol at QB=200: Ca-infusion (200 ml 10% CaCl2 + 0.8 L 0.9% saline) dosing**

1. **Select the base Calcium-infusion Table 1 Rate at QB=200:** The amount of calcium removed from the circuit blood by the dialyzer is altered by the hemoglobin (Hb) and albumin level. The initial calcium infusion rate is prescribed by the PI based on the last laboratory hemoglobin and serum albumin using Table 1. At start the nurse adjusts the initial Ca-infusion Table 1 Rate using the Crit-Line online optical hemoglobin value and the last serum albumin and confirms any change with the PI. The systemic ionized calcium at 1 hour is charted but not used to alter the initial rate. An offset is always applied to the Table 1 Rate based on the hourly net ultrafiltration rate (see below).

Table 1 ACD-A (Citrate) Infusion Fixed Rate, Blood flow = 200 ml/min, ACD-A flow = 400 ml/hour

Rate in ml/hour of the Ca-infusion (20 gm CaCl₂ + 0.8 L 0.9% saline). The rate is defined by the systemic albumin and hemoglobin at a blood flow of 200 ml/min.

Hb	6-6.9 g/dL	7-7.9 g/dL	8-8.9 g/dL	9-9.9 g/dL	10-10.9 g/dL	11-11.9 g/dL	12-12.9 g/dL	13-13.9 g/dL	14-14.9 g/dL	15-15.9 g/dL
Albumin										
0.0-0.7 g/dL	110	106	102	98	93	90	86	82	78	73
0.8-1.2 g/dL	116	112	108	103	99	95	91	87	82	78
1.3-1.7 g/dL	122	118	113	109	105	100	96	91	87	82
1.8-2.2 g/dL	129	125	120	115	110	106	101	96	91	87
2.3-2.7 g/dL	136	131	126	121	116	111	106	101	96	91
2.8-3.2 g/dL	142	137	132	127	121	116	111	106	101	96
3.3-3.7 g/dL	149	143	138	132	127	121	116	111	105	100
3.8-4.2 g/dL	155	149	144	138	132	127	121	116	110	104
4.3-4.7 g/dL	162	156	150	144	138	132	126	120	115	108
4.8-5.2 g/dL	168	162	156	150	144	137	131	125	119	113

2. Adjust the base Ca-infusion Table I Rate at QB=200 using systemic hemoglobin changes The systemic hemoglobin (Hb) level in the arterial limb of the blood circuit will be continuously measured and displayed by an optical sensor (Crit-Line III).

The Hb level may decrease due to bleeding and increase due to blood transfusions or hemoconcentration due to excessive ultrafiltration. If the Hb increases, the circuit plasma flow will decrease and the dialyzer calcium losses will decrease, therefore the calcium infusion rate must be decreased. If the Hb decreases, the circuit plasma flow will increase and the dialyzer calcium losses will increase, therefore the calcium infusion rate must be increased.

The Hb based adjustments are done when a Hb-range change is observed or at least every 20 minutes independent of other adjustments. Select the new base Ca-infusion rate for the hemoglobin range (column) corresponding to the last optical Hb value from Table 1. Use the most recent albumin level to find the appropriate row. Apply the Total Current Offset to the base Ca-infusion Table I Rate to get the final Ca-infusion rate (see below).

3. Offset the base Ca-infusion Table I Rate at QB=200 using the hourly net ultrafiltration rate: Circuit Ca losses due to net ultrafiltration need not be replaced. Calculate the hourly net ultrafiltration rate: [Pre-

dialysis weight (kg) — estimated dry weight (kg)] * 1000 / 4 (hours) = Net ultrafiltration rate (ml/hour). The base Ca-infusion Table 1 Rate is always decreased by 1 ml/each 100 ml/hour net ultrafiltration rate, e.g in table 2:

Table 2 QB=200: Use the net ultrafiltration rate to adjust the base Table 1 Rate of the Ca-infusion (200 ml 10% CaCl₂ + 0.8 L 0.9% saline) at a blood flow of 200 ml/min

The Patient's Hourly Net Ultrafiltration Rate	Calcium Infusion Table 1 Rate Offset for Hourly Net Ultrafiltration
Net UF 100 ml/hour	Offset Table 1 Rate DOWN by 1 ml/hr
Net UF 700 ml/hour	Offset Table 1 Rate DOWN by 7 ml/hr
Net UF 1300 ml/hour	Offset Table 1 Rate DOWN by 13 ml/hr

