6.3.13 Required Documentation

The following items need to be recorded:

- A. Time of SCD cartridge hook-up.
- B. Time of SCD system integration with hemodialysis system.
- C. Visual inspection of SCD system upon initiation of perfusion.
- D. Calcium levels in blood samples and other parameters as required during Citrate anticoagulation therapy per University of Michigan protocol.
- E. System pump speeds every hour.
- F. Adjustments in IV pump infusion rates.
- J. Time of cessation of SCD therapy.
- K. Any unanticipated occurrences should be recorded in hourly comment sections.

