8.3.1.1 Perform 2 D echo

8.3.1.2 Prepare a heparin or citrate intravenous infusion per hospital routine to use with a standard volumetric programmable pump and Crit-Line III online hematocrit measurement device if required by the citrate protocol.

- 8.3.1.3 Assemble blood drawing supplies, including ice bucket, and label tubes.
- 8.3.1.4 Assemble and set-up Study Circuit.
- 8.3.1.5 For Subjects with AV fistula or graft, access with needles or venous cannula (i.e., angiocatheters) according to Investigator orders or per hospital routine.
- 8.3.1.6 For Subjects with tunneled catheters, aspirate heparin flush according to Investigator orders or per hospital routine.
- 8.3.1.7 Review medical history.
- 8.3.1.8 Review concomitant medications.
- 8.3.1.9 Obtain BP, RR, and HR, weight without shoes or over clothes, and oral temperature. Perform physical exam.
- 8.3.1.10 Obtain blood for albumin according to instructions in **Appendix 2**.
- 8.3.1.11 Obtain blood for basic metabolic panel according to instructions in **Appendix 2**.
- 8.3.1.12 Obtain blood for CBC with differential and platelets according to instructions in **Appendix 2**.
- 8.3.1.13 Obtain blood for systemic soluble markers according to instructions in **Appendix 2**.
- 8.3.1.14 Obtain blood for flow cytometry according to instructions in **Appendix 2**.

Initiate the Study Hemodialysis Treatment (SHH or SCD Treatment)

- 8.3.1.15 Begin intravenous heparin infusion as prescribed by standard protocol (*for SHH treatment, heparin will be used for the entire duration of the procedure. For the SCD treatment, heparin will be used only during the first hour of the SCD treatment.*)
- 8.3.1.16 Turn on blood pump at the speed prescribed by the Principal Investigator. Turn on the calcium infusion per protocol.
- 8.3.1.17 Obtain BP, HR, and RR.

Repeated Procedures During Entire Study Hemodialysis Treatment (SHH or SCD Treatment)

- 8.3.1.18 Record Adverse Events.
- 8.3.1.19 Record concomitant medications.
- 8.3.1.20 Adjust heparin flow rate as needed for SHH or calcium chloride administration rate for SCD treatment protocol to maintain systemic iCa level between 1-1.3 mM during the citrate anticoagulant therapy. Document the pre-SCD filter ionized Ca as required.
- 8.3.1.21 Observe cartridges for evidence of hemolysis, clotting, and leakage hourly.

At 1 Hour into Study Treatment Protocol (For SCD Treatment Only)

- 8.3.1.22 Obtain blood for iCa with i-STAT, a bedside diagnostic device (Abbott Labs).

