Appendix 2. Laboratory Analyses

Test	Specimens	Volume (mL)	Total volume (mL)
Albumin	No additive	1 ml	1 ml
Basic metabolic panel	No additive	2 ml	8 ml
iCa*	No additive	0.5 ml	3 ml
CBC and plt	EDTA	3 ml	18 ml
Systemic soluble markers	EDTA	11 ml	66 ml
Leukocyte flow cytometry	EDTA	1 ml	6 ml
Quantitative bHCG	Red top or SST tube	0.5 ml	0.5 ml

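### Section 6.3.4 gives two different intervals for adjusting the calcium infusion to hemoglobin: hourly in one place, and at each range change or no less often than every 20 minutes in another

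*Combined protocol and SAP*

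**What the plan says.** **Hemoglobin interval.** Section 6.3.4 opens with bullets describing the citrate method. The last reads: "The calcium infusion is adjusted hourly based on online hemoglobin values and every time a systemic ionized calcium measurement is performed". Later in the same section, step 2 of the dosing procedure explains that an optical sensor displays hemoglobin continuously, and then states: "The Hb based adjustments are done when a Hb-range change is observed or at least every 20 minutes independent of other adjustments". The new rate is read from the matching Table 1 column, using the latest albumin for the row.

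**Named protocol.** Section 6.3.4 says that "The specific clinical protocol developed at Henry Ford Hospital" will be used for citrate. The list of items to record in Section 6.3.13 includes calcium levels and other parameters "as required during Citrate anticoagulation therapy per University of Michigan protocol".

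**Albumin.** Section 8.3.1.10, among the steps before each study treatment, says "Obtain blood for albumin according to instructions in" Appendix 2. Section 8.3.1 has identical procedures at both treatments, and Appendix 1 repeats its treatment-day procedures on each treatment day. The Appendix 2 line is "Albumin No additive 1 ml 1 ml", that is, 1 ml per draw and 1 ml in total.

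**The concern.** The calcium infusion replaces what citrate and calcium-free dialysate remove, and Section 6.3.4 ties it to systemic clotting and cardiac function. One section gives two intervals for the same adjustment, and the bullet does not present its hourly interval as a minimum. Two members of staff relying on different parts of the section could therefore run different rates in the same patient. Hemoglobin column changes are plausible in this trial: Section 6.3.4 itself says that hemoglobin rises with hemoconcentration under excessive ultrafiltration, and Section 3 describes a population needing aggressive ultrafiltration. The other two items leave a reference and a volume total out of step with the rest of the document.

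**Working it through.** **Inputs.** Citrate phase: the last 4 hours of the 5-hour session (Section 4.1). Intervals: 60 minutes (6.3.4, bullet) and 20 minutes (6.3.4, step 2). Rates: Table 1. Draw volumes and totals: Appendix 2. Draw times: Section 8.3.1 and Appendix 1.

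**1. Number of scheduled hemoglobin reviews = phase length / interval.**
- Bullet: 240 / 60 = 4.
- Step 2: 240 / 20 = 12, plus any prompted by a range change, so at least 12.

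**2. Value of one hemoglobin column = difference between neighboring columns in a Table 1 row.**
- Smallest step: 93 − 90 = 3 ml/h (albumin 0.0-0.7). Largest: 115 − 108 = 7 ml/h (albumin 4.3-4.7).
- Relative to the starting rate, the range is 4/129 = 3.1% to 5/78 = 6.4%.
- Entry requires hemoglobin of at least 9 g/dL. If albumin is assumed to lie between 2.8 and 4.7 g/dL, the steps are 5 to 7 ml/h.
- Example: at hemoglobin 11-11.9 and albumin 3.3-3.7 the rate is 121 ml/h. One column higher gives 116, a change of 5/121 = 4.1%.

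**3. How long a missed column could last.** Counting only the timed reviews, a change could wait up to 60 minutes under the bullet and up to 20 under step 2, a difference of up to 40 minutes. In volume, that is 3 × 40/60 = 2 ml to 7 × 40/60 = 4.7 ml of infusate per column change. Against a range change acted on at once, the delay is up to 60 minutes, or 3 to 7 ml.

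**4. Direction.** Section 6.3.4 says that higher hemoglobin lowers dialyzer calcium loss and therefore the rate needed. A missed rise leaves the infusion above the Table 1 rate; a missed fall leaves it below.

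**5. Appendix 2 totals: implied draws = total / volume per draw, against scheduled draws.**

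| Test | Implied | Scheduled |
|---|---|---|
| Basic metabolic panel | 8/2 = 4 | 2 times × 2 sessions = 4 |
| CBC | 18/3 = 6 | 3 × 2 = 6 |
| Soluble markers | 66/11 = 6 | 3 × 2 = 6 |
| Flow cytometry | 6/1 = 6 | 3 × 2 = 6 |
| Ionized calcium | 3/0.5 = 6 | 6 × 1 (SCD session only) = 6 |
| bHCG | 0.5/0.5 = 1 | 1 |
| Albumin | 1/1 = 1 | 1 × 2 = 2 |

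Every row reproduces except albumin. The table does count both sessions, so the albumin total is 1 ml short of the schedule.

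**6. Protocol name.** The only calcium dosing procedure in the document is the one in Section 6.3.4. Section 6.3.13 concerns what is recorded and contains no rate.

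**The case against.** The strongest reply is that the two intervals are compatible. Reviews every 20 minutes also cover each hourly point, the bullet is an overview, and step 2 is the operative instruction. This stands against the reading that staff cannot obey both. It does not remove the inconsistency, because the bullet does not call its interval a minimum and following it alone breaks step 2.

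Four stronger readings are tempting, and the documents do not support them:

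- **A hypocalcemia hazard.** Section 1 describes severe consequences of uncorrected hypocalcemia but calls these potential risks rare. Under ultrafiltration the expected change is a rise in hemoglobin, and missing it leaves calcium above the Table 1 rate.
- **Two competing dosing protocols.** Section 6.3.13 is a documentation list at the site where treatments are given. It offers no alternative rate, so this is an ambiguous reference only.
- **A week-old albumin in the SCD session.** Appendix 2 cancels no draw and does not say which session its single draw belongs to. Section 6.3.4 already directs staff to the last or most recent albumin. A reader might cost a wrong albumin row at 6 ml/h × 4 h = 24 ml (121 against 127 ml/h), but that assumes four hours without correction. Section 8.3.1.20 adjusts calcium to hold systemic ionized calcium at 1-1.3 mM, and samples are drawn at 2, 3, 4 and 5 hours. One limit on this feedback is stated: "The systemic ionized calcium at 1 hour is charted but not used to alter the initial rate".
- **Distortion of the cardiac outcome.** No figure in the documents links a rate difference of this size to wall motion or strain.

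**Conclusion.** Section 6.3.4 is inconsistent on how often the calcium infusion is adjusted to hemoglobin: 4 scheduled reviews against at least 12 over the citrate phase. A missed column is worth 3 to 7 ml/h, about 3% to 6%, in either direction, and the ionized calcium checks limit its effect. This should be corrected because it is an operative rule for a safety-relevant infusion, but the likely effect on any one session is small. The size rests on Table 1 as printed and on a change of one column; the documents do not say how often hemoglobin crosses a column within a session. The protocol reference and the albumin total are editorial: neither supplies a different rate or removes a scheduled draw.

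**What to change.** Reconcile the opening bullet and step 2 of Section 6.3.4 so that one hemoglobin adjustment interval appears. Which interval is right is for the clinical team to decide.

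In the same edit:
- reconcile the protocol named in Section 6.3.13 with the one named in Section 6.3.4;
- reconcile the albumin total in Appendix 2 (1 ml) with the two pre-treatment draws in Section 8.3.1.10 and Appendix 1 (2 × 1 ml = 2 ml).

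The cost is a few sentences of protocol wording and at most 1 ml added to a blood-volume total. Sample size, visits and analysis are unaffected.
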